This task will proceed in two phases: receptive field mapping and the attention task. For both, the display consists of four light gray circular apertures arranged in a square, one in each quadrant of the screen, and all equidistant from a central fixation point (a black "x", with one arm pointing to each aperture); the background is a uniform gray field. For Receptive Field Mapping, the subject will be asked to fixate the fixation point while black and white checkerboards are presented sequentially, for 500 msec each with a 500 msec inter-stimulus interval, in randomly determined order, in each of the four apertures. Independent of the checkerboards, the fixation symbol will unpredictably change from an "x" to a "+" on average once every 5 sec (range 4-6 sec), and subjects will be asked to report each change with a button press. This will be carried out in three 1-min blocks, each featuring 15 presentations in each of the locations during each block, for a total of 3 min of task. (Length of pauses between blocks will be determined by the patient.) Immediately upon the conclusion of the Receptive Field Mapping (when the patient is ready) the Attention Task will be explained to the patient. Each trial begins with two arms of the fixation "x" changing color for 300 msec, with green indicating the aperture in which it is 75% likely that a target will appear, and white the aperture in which it is 25% likely to appear. After a variable cue-target interval (CTI) of 800-1200 msec, the target, a grating of parallel lines that will either be tilted slightly to the left or to the right of vertical, will appear for 33 msec, followed by a screen asking "L or R tilt?", to which the subject responds with a left- or right-handed button press. The intertrial interval will last for 600 msec. Because subjects will be instructed to make their decision as quickly as possible, it is expected that the average trial will last just under 3 sec. Each block will consist of 48 trials (approximately 2min 24 sec), and within a given block, only two opposing locations of the four possible locations will be cued, the other two positions serving as task-irrelevant locations, at which a target will never appear within that block. The two cued positions will be changed every block. To maximize sensitivity for data analyses, we'll hope to acquire a total of 8 blocks worth of data (384 trials), which, without rests, would come to 19 min 12 sec. With rests between blocks, the entire session is expected to take between 25-30 min. (Note that whereas the 3 min of Receptive Field Mapping are necessary for interpreting the data from this study, as few as four blocks of data from the Attention Task would produce the minimal amount of data needed, and so if subjects fatigue or otherwise ask to terminate testing prior to completion of the full set of 384 trials, we will nonetheless have collected a sufficient amount of data within approximately 15 min of data collection.)

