#### Statistical Considerations:

Sub-study A: The analyses will proceed in two stages. The first will be to determine the spatial selectivity of each ECoG electrode by calculating its response, in high-frequency (70-250 Hz) broadband power to each of the four locations stimulated during the Receptive Field Mapping task. Also of interest will be fluctuations in alpha-band power (8-13 Hz), and in phase-amplitude coupling (PAC) between alpha-band oscillations in the ECoG signal and high-frequency broadband power.

Data analysis from the Attention Task will focus on electrodes identified in the Receptive Field Mapping task to be preferentially responsive to one, or a subset, of the four critical locations. For each of these electrodes, values of alpha-band power and PAC will be analyzed as a function of attentional condition: attended (i.e., cued with 75% likelihood); ignored (i.e., cued with 25% likelihood); or irrelevant. Although a recent study has looked at alpha-band power as a function of attended vs. ignored [14], the proposed study will differ from this in two important ways. First, our critical comparison is between ignored vs. irrelevant; second, all conditions in our task will be within the same informational domain and sensory modality (i.e., visuospatial perception), whereas that of [14] spanned both (i.e., it used switches between an auditory and a motor task). Because this previous study collected 190 trials per subject [14], we believe that our design, which will collect a total of 384 trials, will be sufficiently powered to carry out the analyses of interest.

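### Sub-study A: alternating the cued pair every block leaves a one-block average offset between ignored and irrelevant when an even number of blocks is completed, and no block term is planned

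*Combined protocol and SAP*

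**What the plan says.** Under Research Design and Methods, Sub-study A, "the display consists of four light gray circular apertures arranged in a square, one in each quadrant of the screen". For the Attention Task, "within a given block, only two opposing locations of the four possible locations will be cued", with "the other two positions serving as task-irrelevant locations, at which a target will never appear within that block". The order rule is "The two cued positions will be changed every block". The section gives no starting pair, no counterbalancing and no randomised block order.

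On length, the plan says "Each block will consist of 48 trials (approximately 2min 24 sec" and "we'll hope to acquire a total of 8 blocks worth of data (384 trials), which, without rests, would come to 19 min 12 sec". Rests are allowed between blocks. Four blocks are accepted as the minimum "if subjects fatigue or otherwise ask to terminate testing prior to completion of the full set of 384 trials".

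Under Statistical Considerations, Sub-study A, the electrodes analysed are those that respond preferentially to one or some of the four locations. For each, "values of alpha-band power and PAC will be analyzed as a function of attentional condition": attended, ignored or irrelevant. The plan names ignored versus irrelevant as its critical comparison. No block, order or time-on-task term is mentioned.

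**The concern.** A location is irrelevant for a whole block or cued for a whole block. For an electrode tuned to a single location, its ignored trials and its irrelevant trials therefore never share a block. Anything that changes steadily over the session, such as alertness or signal quality, can differ between the two conditions if their blocks differ in average position.

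Under strict alternation they do differ when the number of completed blocks is even, and both block counts that the plan names (eight and four) are even. The direction is fixed for a given electrode by which pair came first. An analysis by attentional condition alone would then carry drift in alpha power or PAC into the critical contrast, at the electrode and single-patient level where the plan intends to draw conclusions.

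**Working it through.** **Plan's own figures.** 8 × 48 = 384 trials. At 144 s per block, 8 × 144 = 1,152 s = 19 min 12 s. Both agree with the plan.

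**Number of pairs.** Four locations in a square give 6 possible pairs. Exactly 2 are diagonal: upper left with lower right (A), and upper right with lower left (B). With two pairs and a change at every block, the only order is A-B-A-B-A-B-A-B, or the same starting with B.

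**Offset.** Mean block position of B minus that of A:

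| Blocks completed | A blocks (mean) | B blocks (mean) | Offset | Share of first-to-last-block drift |
|---|---|---|---|---|
| 8 | 1,3,5,7 (4) | 2,4,6,8 (5) | 1 | 1/7 = 14.3% |
| 7 | 1,3,5,7 (4) | 2,4,6 (4) | 0 | 0 |
| 6 | 1,3,5 (3) | 2,4,6 (4) | 1 | 1/5 = 20% |
| 5 | 1,3,5 (3) | 2,4 (3) | 0 | 0 |
| 4 | 1,3 (2) | 2,4 (3) | 1 | 1/3 = 33.3% |

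The shares differ, but at a constant drift per block the bias at 4, 6 and 8 blocks is the same: one block's drift. For a pair-A electrode the irrelevant blocks come later on average; for a pair-B electrode they come earlier. If a share w of the pooled electrodes is on pair A, the pooled offset is w − (1 − w): 0 at 50:50, 0.5 block at 75:25, and 1 block if all are on one pair.

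**Effect on a two-sided 5% test.** The plan states no test, alpha level or drift size for this contrast, so these are assumptions: trial SD 1, independent trials, the likely-target cue equally often at both cued locations, and linear drift of D over eight blocks. Each cued block then gives 24 ignored trials and each uncued block 48 irrelevant trials.

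- Eight blocks: 4 × 24 = 96 ignored and 4 × 48 = 192 irrelevant trials. SE = √(1/96 + 1/192) = 0.125. Bias = D/7.
- Four blocks at the same drift per block: 48 and 96 trials. SE = √(1/48 + 1/96) = 0.177. Bias is again D/7.

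| D (SD over eight blocks) | Bias (SD) | Type I error, 8 blocks | Type I error, 4 blocks |
|---|---|---|---|
| 0.1 | 0.014 | 5.1% | 5.1% |
| 0.25 | 0.036 | 5.9% | 5.5% |
| 0.5 | 0.071 | 8.8% | 6.9% |
| 1.0 | 0.143 | 20.8% | 12.8% |

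The table treats the trial variance as known to be 1. In practice drift also inflates the estimated variance. At D = 1 and eight blocks, the block values within each condition have variance 5 × (1/7)² = 0.102, so the estimated SD is √1.102 = 1.05. The critical value becomes 1.96 × 1.05 = 2.058 SE against a bias of 0.143/0.125 = 1.143 SE, and the rejection rate falls to about 18%. The same step gives about 8.4% at D = 0.5. The rounded figures of 9% and 18% are used below.

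**Cost of a linear block term under alternation**, with blocks weighted equally. The correlation of condition with block number is 0.218 in size at eight blocks and 0.447 at four. Variance inflation is 1/(1 − r²): 1/(1 − 0.048) = 1.05 and 1/(1 − 0.2) = 1.25.

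**Order A-B-B-A then B-A-A-B.** At four blocks both pairs have mean position 2.5, and at eight both have 4.5, so the offset is 0. If the session stops at five, six or seven blocks, the offset is 0.83, 0.33 or 1.17 blocks in size.

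**The case against.** The case for leaving the plan alone has real substance.

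- **Alternation is already a fairly good order.** Over all 70 balanced eight-block orders the mean absolute offset is 1.4 blocks (maximum 4), against 1 for alternation. A reader might infer that the order is at fault because it is not randomised, but simple randomisation would do worse on average. This stands.
- **The offset is not universal.** A reader might infer that irrelevant always falls a block away from ignored. The blocks interleave, the shift is an average, and it vanishes at five or seven completed blocks, which early stopping permits. This stands.
- **Four-block sessions are not the worst case.** The 1/3 share invites that reading, and packing a full 0.5 or 1 SD of drift into four blocks gives 15% and 43%. That more than doubles the drift per block (D/3 against D/7). Nothing in the documents supports it; at equal drift per block, four blocks are affected less than eight.
- **Drift may be small.** The documents give no drift size. Their remark on fatigue is conditional, and rests are planned. At 0.25 SD or less over the session the effect is negligible.
- **The sign reverses between electrode groups.** A balanced pool cancels the bias. Under the diagonal reading each hemifield holds one location of each pair, so one-sided coverage does not by itself favour a pair. However, the Trial Safety section says placement is decided only on clinical grounds, so balance is not assured, and single-electrode results stay exposed.
- **"Opposing" is not defined.** Diagonal is the natural reading, and a fixed left-right or up-down split would also give two pairs. If any cross-hemifield pairing were allowed there would be four, and alternation would not be forced.

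These points reduce the size and reach of the problem. They do not supply the missing block term.

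**Conclusion.** The point holds as a minor one. If opposing means diagonal, the order rule forces strict alternation, and the critical contrast for a single-location electrode carries one block's drift whenever an even number of blocks is completed, including the planned eight and the minimum four. No stated element of the analysis removes it.

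At eight blocks the bias is 1/7 of the first-to-last-block drift. Type I error is about 5-6% for drift of 0.1-0.25 SD, 9% for 0.5 SD and 18% for 1 SD. At four blocks with the same drift per block, the last two are about 7% and 13%. These figures rest on linear drift of an assumed size, independent trials and balanced cue roles, and apply to a single electrode or to electrodes all on one pair.

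A reader might go further and infer that the comparison is invalid or that the task order must be replaced. The documents do not support that: drift is not quantified, the bias can cancel across electrodes, and an analysis term deals with its linear part.

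**What to change.** In Statistical Considerations, Sub-study A, add block number as a linear covariate in the ignored-versus-irrelevant comparison of alpha power and PAC. This removes linear drift at every stopping point.

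In the Sub-study A task description, state which pairs count as opposing and alternate the starting pair across patients. That reverses the sign of the offset between patients but leaves the offset within each patient, so it supports the covariate and does not replace it.

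Optionally, use A-B-B-A then B-A-A-B. This balances linear drift at four and eight blocks without a variance penalty at those counts, but needs the covariate at five to seven blocks, and sometimes cues the same pair in two consecutive blocks.

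The cost is one model term and a line in the task script, with no extra trials or patients. With alternation kept, the covariate raises the variance of the contrast by about 5% at eight blocks and 25% at four. Neither a linear term nor the balanced order is guaranteed to remove curved drift.

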#### Sub-study C: Behavioral task, ECoG recording, and data processing.

The procedure and general design considerations will be similar to those of sub-study B. Experimental procedure: In a first task, subjects will be shown different images i.e., textures, objects, faces, bodies, letters, places, tools, and animals in rapid succession (1 second between images). The subjects will be asked to detect with a button press whether two images repeated consecutively. A block last approximately 5 mins, and 2 blocks will be performed. The first one will present the images as cut outs while the second block will present the images in their context, as well as famous faces and places. In a second task, we will present to the subjects five times 2 minutes of rapid presentation of syllables forming non-words. In one series, the syllables will be presented in a random order. In the second series, the syllables will be presented in a structured order with groups of 3 syllables systematically following each other (although different groups of 3 syllables will still be presented in different orders). After the second session, subjects will be tested for their recall of linked order between different syllables. After this test session, the subjects will be explained that the sequence in fact contains words made of 3 syllables and presented this sequence again. Finally, after this last session, subjects will be tested for 3 syllables sequences recognition. In a third task, the subject will be presented with barely perceptible stimuli. After a variable delay, the subject will be asked to report perception of each stimulus and identify its location. For the auditory version of the task, the subject will be asked to wear earphones or earbuds and will be presented with a barely perceptible sound embedded in background noise. After a variable delay, the subject will be asked to report perception of the sound and identify a characteristic of the sound (e.g., the perceived location, perceived pitch, etc.). Between each block of trials, the subject will fixate on a cross on the computer screen. Subjects are shown their cumulative accuracy regarding the location of the stimuli after each block. The behavioural sessions will last 60 minutes, including breaks. Subjects may be asked to wear an eye tracker during the perceptual awareness task. Total session time may take up to 90 minutes per task to include set-up time with image acquisition equipment. The session may be split into two sessions depending upon how the subject is feeling.

Data collection and processing. Clinical monitoring of the “invasive EEG” (the common clinical term for ECoG) is implemented around the clock by the surgical team of the UW Comprehensive Epilepsy Program using a 128-channel Natus NicoletOne clinical monitoring system. Signals from the invasive EEG electrodes are fed simultaneously to two amplifiers, one for the clinical system and one for the research system via splitter connectors. The research system is a 128-channel Blackrock Microsystems NeuroPort System. To ensure that the clinical and research systems do not interfere with each other, the two systems typically use separate ground channels. In the context of EEG, the “ground” electrode can be any electrode, or set of electrodes, that is part of the recording array, but that is not recording from the region of interest. It is typically an electrode that is attached to a portion of the body that is away from the brain, such as the mastoid bone of the skull, or the ear. Additionally, there is a “reference” electrode, which is located on the scalp. In a differential amplifier, the EEG signal is the result of a subtraction of the voltage between the active electrodes and the ground, and the voltage between the active electrodes and the reference. This has the effect of removing spurious environmental electrical fluctuations from the EEG. In every patient’s montage of electrodes there will be several candidate channels from which to select the ground (redundancy being an important precaution for clinical EEG), and so selecting a channel to serve as the ground for the experimental recordings will not in any way interfere with the clinical recordings, nor does it require the placement of electrodes that would not otherwise have been used for the clinical procedure. Note that, to get to this point, the patient was determined to have met inclusion and exclusion criteria prior to the surgical procedure, and so no demographic data are linked to the invasive EEG data. Knowledge of the

placement of the invasive EEG electrodes in the brain, however, is of critical importance to both the clinician and the researcher, and so information about the precise location in the brain of every invasive EEG electrode is merged into to the EEG data set at an early stage of preprocessing, after the data have been collected.

The research system only exists “downstream” of the splitter connectors, and so doesn’t interfere with the clinical recordings in any way. Furthermore, because the system is safety-rated and FDA-approved for invasive recordings, it does not pose any potential risk to the patient. It will have a very low noise-floor in the high-frequency range in which the signals of interest are found, and comes with an SDK that allows the signals to be integrated with custom-written research software. In order to capture the high-gamma signal accurately, we will acquire signals at 1200Hz sampling rate, which is considerably higher than that of the typical EEG experiment or that of many clinical monitoring systems. A built-in low-pass filter automatically prevents aliasing of signals higher than the digitizer can capture. The raw data will be stored on a computer server dedicated to the PI’s research project, that is housed in the Department of Neurological Surgery. All post-acquisition data processing will be performed in the PI’s laboratory facilities in the Dept. of Psychology and the Dept. of Psychiatry. Prior to transfer to the PI’s lab, all data files will be renamed with a code that does not contain any identifying information (e.g., name, sex, age, date of acquisition).

Data analyses and predicted outcomes.

Data and Safety Monitoring Plan:

The DSMP that follows (in 5 sections) was submitted to the NIMH on 05/06/16, and the PI received confirmation of its approval on 06/10/16.

### 1. Summary of the Protocol

The Specific Aim of this study is to test the hypothesis, with electrocorticography (ECoG) recorded from neurosurgical patients, that unattended memory items (UMIs) are represented in phase angle-segregated patterns of activity in the high-gamma band (80-150 Hz), and that attentional prioritization within working memory is implemented via a mechanism of phase-encoded selection.

The **Study Design** entails the collection of ECoG signals, and of button-press responses (accuracy and reaction time, hereafter “behavioral data”) from patients while they perform a cognitive task. The cognitive task consists of viewing test stimuli being presented on a laptop computer, and responding to these stimuli via button presses on a response box that is connected to the laptop computer. Details about the cognitive task are presented in the IRB protocol and in the grant proposal. The cognitive task will consist of 40 trials (i.e., 40 responses) that will last for a span of 21 min 20 sec if administered in a continuous, uninterrupted block of time. However, the task can be interrupted and restarted as needed to suit the comfort of the patient.

The cognitive task will be administered a minimum of 48 hours after surgery to place the ECoG electrodes, and then only at the discretion of the neurologist, and of the patient. The cognitive task will be administered in the patient’s room in the in-patient facility of the University of Wisconsin–Madison Video-EEG Telemetry (VET) Unit. Testing will occur at a time of day of the patient’s choosing, so long as this time conforms with the treatment schedule in the inpatient ward, and it is at minimum of one hour after the time that the subject would routinely wake up in the morning and a minimum of one hour prior to the time that the subject would routinely go to sleep.

The **Primary Outcome Measures** will be the results of analyses of the ECoG signals in relation to the behavioral data. The outcome measures have relevance to basic-science questions about the neural bases of cognitive functions, and have no relation to or significance for the clinical care of the patients enrolled in the study.

The **Sample Size** is four (4) patients. Subjects will consist of patients between the ages of 18 and 65 admitted to the UW Comprehensive Epilepsy Program who have undergone surgical implantation of subdural electrode arrays to better define their seizure focus.

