
Sub-study B: Behavioral task, ECoG recording, and data processing.

Experimental procedure. The study consists of two sessions on different days. The generic task design will be as follows: In the first session, each trial begins with a fixation cross and serial presentation of two sample items, followed by a brief delay (Delay1pre-cue), followed by a cue (Cue1) indicating which item will be tested first, followed by an additional delay (Delay1post-cue), followed by a memory probe

requiring a “same/different” response (Probe1) followed by Delay2pre-cue, Cue2, Delay2post-cue, and Probe2. The timing will be as follows: Fixation (.5 sec); Sample1 (.5 sec); ISI (.1 sec), Sample2 (.5 sec); Delay1pre-cue (.5 sec), Cue1 (.5 sec), Delay1post-cue (2.5 sec), Probe1 (2 sec); Delay2pre-cue (.5 sec); Cue2 (.5 sec); Delay2post-cue (2.5 sec); and Probe2 (2 sec). Thus, total time per trial = 12.6 sec. (Note that the duration of the Delaypost-cue epochs is necessitated by the fact that behavioral [31, 45] and EEG data [31] indicate that it takes between 1-2 sec for an item to transition from AMI to UMI.). This timing will allow for the collection of 96-106 trials within a span of 30 min, a block that can be interrupted and restarted as needed to suit the comfort of the patient. (Previous experience from ECoG studies performed by colleagues of the PI who are based at the University of California indicates that the “20-min mark” is a conservative estimate of the duration of a testing session that a patient can be expected to tolerate; many patients can tolerate either longer sessions, or multiple sessions separated in time.) Critically, the ECoG study that discovered and characterized the phase-encoded selection mechanism that we will investigate in the present study [70] made this discovery in data from four patients, with a design that yielded 40-50 trials/condition/patient; thus our design, intended to collect a minimum of 96 trials, will be adequately powered to detect effects of interest at the single-subject level. (SNR of ECoG signals will be considered further along in this section.)

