As indicated earlier in this protocol, the ECoG study that discovered and characterized the phase-encoded selection mechanism that originally motivated our decision carry out these ECoG experiments [70] made this discovery in data from four patients, with a design that yielded 20-30 trials/condition/patient; thus our design, intended to collect a minimum of 40 trials, will be adequately powered to detect effects of interest at the single-subject level. We note, however, that during his sabbatical year (spent in the lab that published [70]) the PI has observed that as many as double (or more) the final number of subjects desired for an experiment need to be recruited and to participate in it. This is due to several reasons, among them that the ECoG recordings can be contaminated with some much noise that the data are not interpretable, or because a patient's behavioral performance is too poor. Thus, for this sub-study, we plan to enroll 10 patients, with the intent of needing interpretable data from 4.

Sub-study B: The analyses will proceed in two stages. The first will be to identify stimulus-selective electrodes, the second, to test the phase-encoded selection hypothesis. That is, although the overarching motivation for this research is to test the idea that the mechanism of phase-encoded selection governs the attentional prioritization of one among multiple items held in working memory, we

will first need to determine the physiological code, carried by the ECoG signal, with which items are represented in working memory.

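### The monitoring plan gives the sample size as 4 patients, but 4 is the evaluable target; the statistics section plans to enrol 10 in each of Sub-studies A and B

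*Combined protocol and SAP*

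**What the plan says.** Section 1 of the DSMP (Summary of the Protocol) gives one figure: the sample size "is four (4) patients". The next sentence describes who is recruited (age range, epilepsy programme, implanted arrays). It does not say that the figure counts only patients with usable data.

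Statistical Considerations gives a different count. The discussion of Sub-study A ends: "Thus, for this sub-study, we plan to enroll 10 patients, with the intent of needing interpretable data from 4". The discussion of Sub-study B ends with the same sentence. Both give the same reason. The investigator has seen that "as many as double (or more) the final number of subjects desired for an experiment" must be recruited and take part, because recordings can be too noisy to interpret "or because a patient's behavioral performance is too poor".

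The DSMP is presented as current text. Its introduction says that it "was submitted to the NIMH on 05/06/16, and the PI received confirmation of its approval on 06/10/16". Sub-study C has a described procedure but no stated number of patients.

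**The concern.** Two sections in force give different sizes, and nothing in the text available reconciles them. In a monitoring plan, a sample size without a qualifier will be read as the number of people who enter the research. That is also the number that matters there, because the DSMP's provisions on consent, privacy and adverse-event reporting apply to everyone enrolled. The patients beyond the fourth are not screened out beforehand. By the protocol's own account they are lost after taking part, through noise or poor performance, so they have already consented, been tested and had data stored.

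What is at stake is whether the funder that approved the DSMP, and anyone who relies on it, has the right picture of how many patients will be approached and tested.

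**Working it through.** **Inputs**

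- DSMP section 1: 4 patients, type of count not stated.
- Statistical Considerations, Sub-study A: 10 enrolled, 4 interpretable.
- Statistical Considerations, Sub-study B: 10 enrolled, 4 interpretable.
- Over-recruitment: double or more the final number wanted.
- Sub-study C: no number.
- No alpha, power, effect size or standard deviation is given, so the size cannot be checked with a power formula. The check is a comparison of counts plus a binomial calculation.

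**Step 1: does the plan's own 10 follow from its 4?** Enrolment needed = evaluable target / usable fraction.

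- Double, so a usable fraction of 50%: 4 / 0.5 = 8.
- Ten enrolled for four usable: 4 / 10 = 40%, a loss of 60%; 4 / 0.4 = 10.

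Ten is thus consistent with double or more, and the statistics section agrees with itself. The DSMP's 4 equals the evaluable target in that section.

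**Step 2: size of the gap.** The DSMP summary states only the working-memory aim and describes one cognitive task, so its counterpart is Sub-study B: 10 / 4 = 2.5. For A and B together, enrolment is 10 if the same patients do both, and 10 + 10 = 20 if none do. The documents do not say which.

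**Step 3: could 4 be an enrolment figure?** Treat patients as independent, each with the same probability p of usable data. This p is an assumption. The range 40% to 50% comes from Step 1.

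| p | Expected usable of 4 | Chance that all 4 of 4 are usable | Chance of at least 4 of 10 |
|---|---|---|---|
| 0.4 | 4 × 0.4 = 1.6 | 0.4^4 = 0.0256 (2.6%) | 0.618 (62%) |
| 0.5 | 4 × 0.5 = 2.0 | 0.5^4 = 0.0625 (6.3%) | 1 − (1 + 10 + 45 + 120)/1024 = 0.828 (83%) |

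Under the protocol's own account of losses, 4 cannot be the number to enrol.

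**Step 4: is the DSMP summary out of step elsewhere?** It says: "The cognitive task will consist of 40 trials (i.e., 40 responses) that will last for a span of 21 min 20 sec". That is (21 × 60 + 20) / 40 = 1280 / 40 = 32 seconds per trial. For the first session of Sub-study B the protocol says "Thus, total time per trial = 12.6 sec", with 96 to 106 trials. This suggests that the summary as a whole was not updated with the protocol, but does not prove it.

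**The case against.** The strongest reply is that the figures do not conflict. The DSMP never calls 4 an enrolment figure, and 4 is the correct evaluable target, so only a label is missing. Enrolment is set in the statistics section, which plans openly for over-recruitment, and nothing makes 4 a cap. The monitoring provisions would also work the same at 4 or at 10: there are no trial-stopping rules, stated risks are limited to loss of privacy, and events are reported on fixed timelines.

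Most of this stands, and it limits the point. It does not remove it, because the label is absent exactly where a reader needs the number enrolled.

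Three stronger readings are tempting, and the documents do not support them:

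- **That the DSMP is wrong by a factor of five.** This sets 20 against 4. It brings in Sub-study A, which the DSMP summary does not describe, and assumes that no patient does both tasks. The like-for-like gap is 2.5-fold.
- **That safety monitoring is wrongly sized, or that the study will miss its target.** No visible monitoring rule depends on the number of patients, and recruitment follows the statistics section. The low probabilities for 4 enrolled show only that 4 cannot mean enrolment. The text between DSMP sections 1 and 3 was not available for this review, so these statements cover the visible text only.
- **That the chances are simply 6% and 83%.** Those figures rest on a 50% usable fraction, while the protocol offers an informal observation with no upper limit. The plan's own ratio of 4 to 10 gives 2.6% and 62%.

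**Conclusion.** The point holds as an inaccurate figure in an approved monitoring plan. The DSMP reports the evaluable target as the sample size and so understates planned enrolment 2.5-fold for its closest counterpart. The comparison of counts needs no assumption beyond matching the DSMP summary to Sub-study B. The total of 10 to 20 for A and B depends on unstated overlap. The probabilities depend on an assumed usable fraction of 40% to 50% and on independence between patients.

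The practical effect is modest. It concerns how accurately the monitoring plan states the number of patients who will consent and be tested. It is not a flaw in the design, and it does not show any added risk to patients.

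**What to change.** Replace the single figure in DSMP section 1 with wording such as: *planned enrolment of 10 patients in Sub-study A and 10 in Sub-study B, to obtain interpretable data from 4 in each*. Keep it as a planned number. Calling it a maximum would set a ceiling that sits badly with the protocol's expectation of double or more.

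In the same amendment:

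- say whether the same patients serve Sub-studies A and B, so that the total can be read off;
- state the number for Sub-study C separately, since none is given and it should not be inferred from A and B;
- compare the DSMP's task description with Sub-study B and reconcile the two.

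The cost is an amendment to the DSMP text and a notice to the funder that approved it. No patients are added to the current plan for A and B, and no analysis changes.
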